### Women found pregnant at baseline

If pregnant, the research assistant will inform the woman of the test results alone, unless the woman prefers for them to be delivered with her husband present. The research assistant will then provide brief couples counseling on the importance of prenatal care, having a skilled attendant at birth, and breastfeeding, provide an information sheet with a list of nearby health facilities offering free prenatal care, and a paper referral to the couples' preferred health facility. She and her partner will be withdrawn from the study and informed of their withdrawal.

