#### Pregnancy test procedures

At the baseline home visit, after consent is obtained from both partners, we will conduct a pregnancy test. Though the eligibility screening questions asks women if they are currently pregnant, we will conduct the test to confirm. The consent form will inform women that if the pregnancy test is positive, they will not be able to continue participation in the study. The pregnancy test will be a Human Chorionic Gonadotropin (HCG) urine test strip, which requires the woman to urinate in a cup (provided by research staff) and immerse the strip in the cup vertically. The woman will be instructed to urinate in the cup by the research assistant and bring the cup to the research assistant afterward and will be given privacy to do so. The research assistant will immerse the strip in the cup and will read the woman her results (~10 minutes later). If the woman is unable to urinate at the time, the research assistant will schedule a time to return to conduct a second test. If the results are invalid, the research assistant will immerse the strip for longer, conduct a second test, or schedule a time to return to conduct a second test. If the pregnancy test is negative (our final eligibility criterion), the research assistant will conduct the baseline questionnaire with each partner separately either in the home or another agreed upon location. The research assistant will ensure that each partner in the couple have full privacy when completing the questionnaire. If they do not, the research assistant will reschedule the interview for another time. During the 6-month follow-up visit, women fill follow these same procedures. The 6-month visit pregnancy test is used to measure change in incidence of unintended pregnancies. The pregnancy test results will be double entered by the research assistant into a KoboCollect data file upon receipt.

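### A positive baseline pregnancy result goes to the woman alone by default, but the unconditional couples counselling and referral that follow reveal it to her husband whatever she wishes

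*Combined protocol and SAP*

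**What the plan says.** The section Pregnancy test procedures places the test at the baseline home visit: "after consent is obtained from both partners, we will conduct a pregnancy test". The test closes the eligibility assessment: "If the pregnancy test is negative (our final eligibility criterion), the research assistant will conduct the baseline questionnaire with each partner separately". The same section reports that the consent form tells women that "if the pregnancy test is positive, they will not be able to continue participation in the study".

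What follows a positive test is set out in Women found pregnant at baseline, in this order:

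- **Result.** "the research assistant will inform the woman of the test results alone, unless the woman prefers for them to be delivered with her husband present".
- **Counselling.** "The research assistant will then provide brief couples counseling on the importance of prenatal care, having a skilled attendant at birth, and breastfeeding".
- **Referral.** An information sheet on nearby facilities with free prenatal care, and "a paper referral to the couples' preferred health facility".
- **Withdrawal.** "She and her partner will be withdrawn from the study and informed of their withdrawal".

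Only the first step depends on what the woman prefers.

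**The concern.** A woman who hears her result alone has been given a private moment and, implicitly, some say in whether her husband is involved. The next instruction takes that say away. Staff who follow the section as written go on to counsel both partners on topics that make sense only if she is pregnant. The husband then learns of the pregnancy through an act of the study.

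The plan's own content shows why this deserves care. Women are asked at screening whether they are pregnant and enrol as not pregnant, so a positive test is either new to the woman or something she had not shared. Inclusion criterion 8 requires only one member of the couple to want to avoid pregnancy for at least a year, so the two may disagree. Recruitment & Sampling goes to some length to question partners separately on fertility preferences and contraception. Monitoring Intimate Partner Violence (IPV) recognises that sensitive discussions between partners can lead to conflict. What is at stake is participant safety and confidentiality, not an estimate or a test.

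**Working it through.** No arithmetic applies, and the plan gives no figure to reproduce. The check is to follow the section step by step for each preference the woman may express.

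| Step | She prefers her husband present | She hears the result alone (default) | Does the text vary the step? |
|---|---|---|---|
| Result | Given to both | Given to her only | Yes |
| Counselling | Given to the couple | Given to the couple | No |
| Referral | To the couple's preferred facility | To the couple's preferred facility | No |
| Withdrawal notice | Given to both | Given to both | No |

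**Counselling.** It covers prenatal care, birth attendance and breastfeeding, it is addressed to the couple, and it comes after a pregnancy test at the same visit. A husband who takes part learns the result. This is direct disclosure, and it is enough to carry the point.

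**Referral.** A referral for prenatal care to a facility that the couple prefers presupposes that he knows, because his preference has to be sought.

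**Withdrawal notice.** The section does not say what reason, if any, the partner is given. Because a negative test is the final eligibility criterion and the test follows both partners' consent, exclusion at that moment points to a positive test. This route works by inference only.

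**Search for another branch.** Four other sections were read for a rule that would change the right-hand column.

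- Recruitment & Sampling provides privacy for screening questions, not for test results.
- Pregnancy test procedures gives the woman privacy when she provides the sample and has the research assistant read her the result, but is silent on the husband.
- Participant contact lists concerns contact details.
- Monitoring Intimate Partner Violence (IPV) concerns participants in the intervention.

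None supplies an alternative.

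**Order of information.** History of partner violence is part of the baseline data. The baseline questionnaire follows a negative test. For a couple with a positive test, the disclosure would therefore come without staff having collected that history, and the couple then leaves the study.

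**The case against.** The strongest reply is that the section does not contradict itself. Its first sentence governs who is in the room when the result is given. It does not promise that the husband will never know. A research assistant can tell the woman alone, then counsel the couple, then inform both of withdrawal, and will have obeyed every sentence. Hearing the news first and in private has value of its own. This stands. A reader might infer a literal contradiction, or that the privacy protection never works; the text supports neither.

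Other parts of the reply also stand:

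- A reader might infer that disclosure comes within minutes. The section gives an order of steps and no interval.
- A reader might treat the withdrawal notice as disclosure in itself. The document says that women are told a positive test ends participation; it does not say that the husband is given that reason.
- Private delivery is the default, so those who hear alone include women content for their husbands to learn next. They cannot all be counted as harmed.
- Couples excluded at baseline attend no sessions, so the absence of post-session conflict checks follows from exclusion and is not a further defect. The IPV section also expects the risk to be low.
- The consent form, the recruitment script and the Protection of Human Subjects section to which the IPV section refers are not available. Any of them might settle the matter.
- The Data Analysis Plan is written in the past tense, so baseline testing may be complete.

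What the reply does not remove is the missing branch. For a woman who does not want her husband told, the section as written requires a step that tells him, and it refers to no other document that would say otherwise.

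**Conclusion.** The point holds as a procedure that defeats its own privacy option. Couples counselling and referral are unconditional and disclose the pregnancy to the husband regardless of the woman's wishes; the withdrawal notice may add to this by inference.

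Its size cannot be given. The document states neither how many women test positive at baseline nor how many of those would not want their husbands told, and any rate would be a bare assumption. There is no effect on the statistical analysis.

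The conclusion assumes that the section is the working instruction for this situation and that the unavailable consent and human-subjects text does not modify it. If that text does set out how the partner is involved, what remains is a missing cross-reference. The change is still worth making, because it costs little and the disclosure would be caused by study staff. If baseline testing is over, it matters for any reuse of the procedure after this pilot.

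**What to change.** Reconcile the sentences of Women found pregnant at baseline so that each partner-facing step (joint counselling, the referral, and any reason given for withdrawal) is consistent with the woman's stated preference about her husband's involvement. State explicitly what happens to each step when she hears the result alone. If the consent form or the Protection of Human Subjects section already covers this, cite it there. The content of the counselling and the place of referral are for the investigators; the request is only that the steps agree with one another.

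The cost is a few sentences in the protocol and matching instructions for the research assistants. The small downside is that some partners would receive a less specific explanation of why the couple is leaving the study. Some may still infer the reason from the timing of the test, so the change reduces the problem without removing it.

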#### Participant contact lists

Participants will also be told that any contact information they provide will be recorded on their contact form which will be kept in a locked filing cabinet in a locked room at the clinic. Their contact information will be compiled into a list with other participants for staff to use when they make phone calls, so that they know who to contact. Participants will be made aware that this list will not contain any information regarding any sensitive information collected from them. During the

consent process, participants will be made aware of the potential risks associated with the above-mentioned retention and tracking procedures, including (1) the possibility of breaches in confidentiality of personal and secondary contact information stored in contact information forms; (2) the possibility of the contact list used by staff to be lost when they are making phone calls; and (3) the possibility of breaches in confidentiality resulting from staff contact attempts (e.g., telephone calls). Verification of comprehension of informed consent associated with retention procedures and their respective risks will be accomplished by asking participants to recall central points of the informed consent. During this consent process, participants will be able to ask the research assistant any questions that they have regarding the retention procedures. This process will verify understanding of informed consent, will clarify points of confusion, and will ensure that the potential risks of participation associated with the retention-promoting procedures are understood and accepted by consenting participants prior to participation.

## Data management

#### Qualitative data

Audio recordings of all qualitative data will be transferred to a password protected computer. All focus group discussions, key informant interviews, and qualitative exit interviews will be transcribed and translated into English and entered into a software analysis system (Atlas.ti). Electronic audio recordings of individual and group counselling sessions will be transcribed within 6 months of the session and the audio recordings will be destroyed once the information from the recordings is written down and double-checked for accuracy.

#### Quantitative data

Questionnaires. Data for the baseline, follow-up questionnaires will be entered in real-time while the interviewers are conducting the interviewer-administered CAPI questionnaires (using KoboCollect software). Using the KoboCollect system also eliminates the possibility of any out of range responses and therefore, data cleaning is not necessary. Data collected using Kobo is easily exported into SPSS and other statistical programs for analysis.

Clinic record abstraction. A research assistant will extract data from medical charts and enter it into a database identified only by study ID number. Extracted data will include date of family planning visit, and type of contraceptive method received. Clinical record data will be double entered by the research assistant into a KoboCollect data file upon receipt. The double entered data will be checked and any discrepancies will be corrected by double checking the clinic records, and by comparisons with the laboratory report.

*Pregnancy test data entry*. The pregnancy test results will be double entered by the research assistant into a KoboCollect data file upon receipt.

## Data safety monitoring plan

The proposed study will conform to rigorous monitoring procedures, standardized reporting of adverse events using Event Report Forms, regular review of the study by the joint-Principal Investigators (PIs), Drs. [name] and [name], and review of the study by a Data and Safety Monitoring Board (DSMB).

The PIs, Drs. [name] and [name], [name], and research staff, will ensure appropriate: (1) conduct of the informed consent process (e.g., that informed consent is obtained before proceeding with study procedures and properly stored), (2) enrollment of study subjects, (3) collection and analysis of data, (4) implementation of study procedures to ensure consistent monitoring of subjects for possible adverse events, (5) review of adverse events and reporting to the DSMB and IRB, and (6) maintenance of the privacy and confidentiality of study subjects. The PIs maintain ultimate responsibility for the project and for the safety of study participants.

[name] and [name] will be responsible for meeting with the research team on a regular basis (weekly, either in person or by conference call) to review the progress of the study and address any human subject issues that occur. These discussions may involve adverse event prevention measures, recruiting of appropriate study subjects, research staff training on protection of human subjects, as well as occurrence of adverse events, unexpected incidents, or protocol problems. The joint-PIs and subcontract PI will meet with the research assistants regularly to go over the progress of the study and communicate any issues or adverse events to the joint-PIs. [name] will compile reports on this information to submit to the PIs and Data and Safety Monitoring Board (DSMB) for review.

## Data Safety Monitoring Board (DSMB)

The DSMB will consist of a committee of experts responsible for reviewing clinical trial data on an ongoing basis to ensure the safety of study subjects and validity and integrity of the data. Members will be independent, with no vested interest in the outcomes of the present study. The board will consist of three members, at least one from Uganda and at least one from the U.S., unless the UTSA or MakSPH institutional review boards recommend a larger committee based on their assessment of the level of risk of the present trial. At a minimum the members will include (1) expert(s) in the clinical aspects of the disease/patient population being studied; (2) one or more biostatisticians; (3) and investigators with expertise in current clinical trials conduct and methodology.

The DSMB will review the study to approve the initial protocol before data collection begins, and every 3 months throughout the duration of data collection activities. We anticipate data collection activities will be completed over an 8 months period, thus the DSMB is expected to meet twice during this period. Before each DSMB meeting, [name] will provide the DSMB with a report containing (1) study progress such as accrual, baseline demographic characteristics, and other general information on study status, and (2) any confidential data on study outcomes, including safety data. This information will allow the DSMB to review and assess the safety of participants and the validity and integrity of the data. Meetings shall be closed to the public because discussions may address confidential patient data, or present unblinded data. Meetings

will be convened as conference calls. An emergency meeting of the DSMB may be called at any time should questions of participant safety arise. The DSMB may request the presence of study investigators at such meetings. A formal report from the DSMB will be supplied to the PIs within 6 weeks of each meeting. Each report will conclude with a recommendation to continue or to terminate the study. This recommendation shall be made by formal majority vote. Any recommendation to terminate the study will be transmitted to the PI, IRB, and NIH as rapidly as possible via a letter from the DSMB Chair/Administrator to the PI for distribution to the institutional official, sponsor, and the local IRBs.

## Monitoring Intimate Partner Violence (IPV)

Though we expect the risk of adverse events resulting from participation in the intervention to be low, since we are working with couples and facilitating discussions around sensitive topics, such as family planning and gender norms, we have developed procedures to closely monitor participants in the couples' intervention. The implementation of these procedures will ensure any unanticipated adverse events related to violence or relationship conflict are identified and addressed immediately. First, our baseline data will assess participants' history of experiencing and perpetrating intimate partner violence. We will use this data to identify couples who report a history of violence, so that intervention facilitators can closely monitor those couples, and pay special attention to issues of violence in the intervention sessions to minimize the risk of conflict arising between couples. In addition, after each couples' session, men and women will separately complete a brief questionnaire to collect process data on the feasibility and acceptability of the intervention. In addition to questions on feasibility and acceptability, this questionnaire will include questions to assess if the intervention had any negative consequences on couples' relationships, either during the intervention itself, or since the last intervention session, whether at home or elsewhere. Items will include a modified 3-item version of the Conflict Tactics Scale to assess experience of emotional, physical, and sexual conflict since the last intervention session. Participants will be asked about the frequency of being the recipient of each type of conflict by their partner, as well as the perpetrator of each type of conflict. The questionnaire will also include an open-ended question to probe further on the occurrence of abuse if any is reported. The responses to this questionnaire will be reviewed immediately by the intervention facilitators, as well as a research assistant. Any indication of potential abuse or conflict resulting from the intervention, whether verbal or physical, will be reported immediately to the Investigators, and follow the plan for reporting adverse events (described below) and a protocol to minimize the risk of future adverse events, determine the safety of the participants' continued participation in the study, and refer the couple to support services (see "Protection of Human Subjects" section) for more details.

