#### **Process Data**

Brief interviews with participants after each session. After each intervention and control session, all couples will complete a brief semi-structured interview (~5 min) to assess acceptability of the intervention content and structure, rating perceived importance and satisfaction with intervention content, and an open-ended question on what they liked and disliked. These brief semi-structured interviews will also include questions to assess any unanticipated negative adverse events occurring because of the intervention (e.g., partner conflict).

**Exit interviews with participants post-intervention**. Within 3-4 weeks of the pilot intervention, brief semi-structured exit interviews (~15 min) will be conducted with intervention participants (n=70), as well with facilitators (n=2), participating health workers (n=2), and community leaders (n~2-4) to further assess acceptability, feasibility, appropriateness, barriers to implementation/utilization, areas for improvement, and progress on "Family/Community Action Plans." Exit interviews can be conducted in-person or over the phone. See Table 3 for more detail on measures of acceptability and feasibility for intervention content and structure.

**Data collection to assess intervention fidelity.** Facilitators will follow a fidelity checklist to ensure all steps are completed, which will also be monitored in early dialogues and then randomly throughout the course of the study through direct observation of intervention sessions by research

staff to allow for immediate feedback. Staff will complete a session checklist on activities conducted, number of participants, engagement, and issues encountered including those related to community leader participation (providing immediate feedback to ensure fidelity). In addition, a randomly selected portion (~20%) of the dialogues will be audio recorded, transcribed, and analyzed for fidelity.

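### Reporting of partner conflict is conditioned on attribution to the intervention and described for one arm, so the adverse-event log alone cannot separate an intervention effect from background conflict

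*Combined protocol and SAP*

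**What the plan says.** Four sections of the combined protocol and SAP deal with partner conflict, and they do not use the same rule.

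- **Monitoring Intimate Partner Violence (IPV).** The procedures are introduced for one group: "we have developed procedures to closely monitor participants in the couples' intervention". After each couples' session, men and women separately complete a short questionnaire: "Items will include a modified 3-item version of the Conflict Tactics Scale to assess experience of emotional, physical, and sexual conflict since the last intervention". Recall thus runs back to the previous session of that arm. Frequency is recorded by type, for both roles. For the recipient role the text is: "Participants will be asked about the frequency of being the recipient of each type of conflict by their partner". Review is then assigned: "The responses to this questionnaire will be reviewed immediately by the intervention facilitators, as well as a research assistant". The trigger for escalation, and for following the adverse-event plan, is: "Any indication of potential abuse or conflict resulting from the intervention, whether verbal or physical, will be reported immediately to the Investigators".
- **Process Data.** Both arms are interviewed: "After each intervention and control session, all couples will complete a brief semi-structured interview (~5 min". The safety content of that interview is "questions to assess any unanticipated negative adverse events occurring because of the intervention (e.g., partner conflict".
- **Adverse events.** The principal investigators review serious and non-serious events monthly and log all of them. The summary for the ethics boards includes relation to study and severity.
- **Data Safety Monitoring Board (DSMB).** The board receives "any confidential data on study outcomes, including safety data". No split by arm is specified.

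The Data Analysis Plan names no conflict or safety analysis. Its secondary outcomes are not listed.

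**The concern.** The IPV section uses baseline data to identify couples with a history of violence, so the protocol itself expects some conflict that has nothing to do with the sessions. Judging cases one at a time cannot separate that background from an effect of the intervention. A concurrent control count, collected in the same way, can at least describe the difference.

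As worded, the route into the adverse-event plan runs through a judgement of cause. No rule is given for making that judgement, and the section describes the route only for couples receiving the intervention. The log can then mislead in two directions. Background conflict attributed to the sessions looks like harm with nothing to set it against. A real excess can disappear if each case is separately judged unrelated. Partner conflict is the one harm given its own monitoring section, so this is the safety count that most needs to be interpretable.

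**Working it through.** No conflict rate, safety sample size or safety power is stated, so there is no figure of the plan's to reproduce. The check is mainly a comparison of the text.

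**Step 1. The sections side by side.**

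| Question | IPV section | Process Data | Adverse events |
|---|---|---|---|
| Which arm? | Intervention couples; control not mentioned | Both | Not restricted |
| Do the questions ask about cause? | Conflict Tactics items: no | Yes, events due to the intervention | Not applicable |
| Recall window | Since the last intervention session | Not stated | Not applicable |
| Role of relatedness | Condition for reporting | Part of the question | Recorded attribute |

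**Step 2. What follows.**

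- Collection is wider than reporting. The Conflict Tactics items gather all conflict, but the reporting sentence passes on only what is thought to result from the intervention.
- Relatedness is an entry condition in one section and a recorded field in another. An event judged unrelated is outside the first rule and inside the second.
- A control participant who takes the Process Data question literally has little to report. The Conflict Tactics recall window is also tied to intervention sessions. No section says that control couples receive those items.
- Neither the DSMB section nor the Data Analysis Plan provides for a table of conflict by arm.

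**Step 3. What counting in both arms could show (illustration).**

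Inputs: the Process Data section gives 70 intervention participants. Assumed: these are 35 couples, the control arm is the same size, two-sided alpha is 0.05, and the background proportion with any conflict is 10%, 20% or 30%. Correlation within villages and within couples is ignored, which is optimistic.

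Power = Φ[(d − 1.96·SE0)/SE1], where d = p2 − p1, SE0 = √(2·p̄(1 − p̄)/n), p̄ is the mean of p1 and p2, and SE1 = √((p1(1 − p1) + p2(1 − p2))/n).

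Example with n = 70 and a rise from 20% to 30%: SE0 = √(2 × 0.25 × 0.75/70) = 0.0732 and SE1 = √((0.16 + 0.21)/70) = 0.0727. Power = Φ[(0.10 − 0.1435)/0.0727] = Φ(−0.598) = 27.5%.

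| n per arm | Background | Power for +10 points | Rise detectable with 80% power |
|---|---|---|---|
| 35 | 10% | 21.3% | 28.5 points |
| 35 | 20% | 15.9% | 32.0 points |
| 35 | 30% | 13.8% | 33.0 points |
| 70 | 10% | 38.0% | 19.0 points |
| 70 | 20% | 27.5% | 22.0 points |
| 70 | 30% | 23.5% | 23.5 points |

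**Step 4. Possible volume of background reports (wholly assumed rates).**

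The training section mentions a session 3, so at least three sessions are assumed. Recall since the previous session then gives two between-session intervals, or three if the first session also looks back. With 10% to 20% of 70 participants reporting per interval:

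- Two intervals: 70 × 2 × 0.10 to 0.20 = 14 to 28 reports. A quarter attributed = 3.5 to 7.
- Three intervals: 70 × 3 × 0.10 to 0.20 = 21 to 42 reports. A quarter attributed = 5.25 to 10.5.

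Neither the rates nor the one-quarter share comes from the documents. These counts show the mechanism and are not an estimate.

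**The case against.** The strongest reply is that the escalation trigger does not delete data. The Conflict Tactics items do not ask about cause. The questionnaire in the IPV section may be the same instrument as the interview in Process Data, since both are brief, follow each session and cover acceptability. If so, conflict data would exist in both arms and could be tabulated. In Process Data, the word intervention may also loosely cover whichever session a couple attended. The Adverse events section logs all events, and recording relation to study would serve little purpose if only related events could be logged. The trigger is also set low, at any indication of potential abuse or conflict, and the causal phrase may qualify conflict only and leave abuse unconditioned.

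Much of this stands. A reader might infer that control-arm conflict can never count, that the control count is zero by rule, or that the trial cannot show whether conflict rises. The documents do not establish any of these. A reader might also infer that facilitators decide cause. The text says that they and a research assistant review the responses; it assigns attribution to no one.

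The reply does not remove the inconsistency. No section says that the two instruments are the same or that control couples receive the Conflict Tactics items. The favourable reading has to be supplied by the reader.

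Three practical objections also carry weight. The same trigger starts the review of continued participation and referral to support, so a wider trigger could change participant management unless logging is kept separate. The Data Analysis Plan is written in the past tense, so changes to collection may come too late. Details are deferred to a section on protection of human subjects that is not in this document.

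**Conclusion.** The point holds in a limited form. Followed as written, the plan makes attribution a condition for reporting partner conflict, describes the conflict items for one arm, and puts a causal question to the other. The Adverse events section treats relatedness differently. The log therefore cannot by itself separate an intervention effect from background conflict, and no by-arm table is planned to supply what the log lacks.

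The stronger conclusion, that the trial can produce no evidence on excess conflict, is not supported, because cause-neutral data may exist in both arms.

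The distortion cannot be sized from the documents. Counting in both arms would not give a powered test either: under the assumptions above, the detectable rise is about 19 to 33 points, and power for a 10-point rise is about 14% to 38%, before any allowance for clustering. The gain is an interpretable description of harm, which suits a pilot. The finding rests on the wording of the sections, not on the illustrative numbers.

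**What to change.** Reconcile the Process Data, IPV and Adverse events sections so that:

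- **(a) Collection.** The same three Conflict Tactics items are asked of each partner separately after every session in both arms, with recall since the last session of whichever arm the couple is in.
- **(b) Logging.** Every positive answer in either arm is logged. Suspected relation to the study is a separate field and not a condition of entry.
- **(c) Reporting.** The DSMB report and the final report tabulate conflict by arm and by baseline history of violence, as estimates with confidence intervals and no claim of a powered test.

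The text should say that this logging does not alter the rules for referral or continued participation, which remain with the investigators.

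If collection is already complete, (a) can no longer be done. The report should then state which conflict items each arm received, tabulate whatever cause-neutral responses exist by arm, and say where the comparison is incomplete.

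The cost is a change of wording and three items in an interview of about five minutes that is already held in both arms. The downsides are more logged events, most of them likely to be background, and disclosures of violence in the control arm that staff must be ready to handle. Any numerical illustration of volume carried into the plan should be labelled as resting wholly on assumed rates.
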